3.2 General study level definitions

3.2.1 Relative day

Two relative days will be calculated, these will be relative to the following *reference dates*; the first relative to the start date of study medication (placebo or bimekizumab) in AS0008 and the second relative to the start date of study medication in AS0009. Relative day will be calculated as:

$$\text{Current date} - \text{reference date} + 1 \quad (1)$$

for dates on or after the reference date, and:

$$\text{Current date} - \text{reference date} \quad (2)$$

for dates before the reference date.

Additional character relative day variables will be derived for inclusion in listings:

$$\text{Current date} - \text{reference date} + 1 \quad (3)$$

for dates on or after the reference date and on or before the end date of study medication (no prefix),

$$\text{Current date} - \text{reference date} \quad (4)$$

for dates before the reference date ('-' prefix), and:

$$\text{Current date} - \text{end date of study medication in AS0009} \quad (5)$$

for dates after the end date of study medication (with '+' prefix).

Relative day will not be calculated if dates are partial or missing.

3.2.2 Study periods

The following study periods are defined:

- Treatment Period: The Treatment Period (204 weeks), starts with the first dose of open-label bimekizumab in AS0009 and ends with the last dose of study medication.
- Dosing period: The dosing period starts at the start date of study medication in AS0009 and ends at 1 dosing interval (28 days) after the end date of study medication.
- Safety follow-up (SFU): The SFU is the period after the last dose of bimekizumab administration with the SFU visit scheduled for 20 weeks after the last dose of bimekizumab.

3.3 Definition of Baseline values

The Baseline value defined in the AS0008 database will be used as a Baseline for AS0009, without additional derivation. The change from AS0008 Baseline will be calculated.

Due to a change in laboratory vendor between AS0008 and AS0009, laboratory values (with the exception of CRP) will use the AS0009 Laboratory Baseline, defined as the earliest post-EV value recorded in AS0009 at or prior to AS0009 Week 12 (excluding any local laboratory measurements). Change from AS0009 Laboratory Baseline will be calculated for these parameters. Change from Baseline will not be calculated for local laboratory measurements as there is no Baseline defined for these values.

The CRP values from the two laboratory vendors have been calibrated, so change from AS0008 Baseline will be calculated for CRP.

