2.2.1.3 Other safety variables

Other safety variables are:

- Change from AS0009 Laboratory Baseline (as defined in [Section 3.3](#)) in clinical laboratory variables (hematology and biochemistry, with the exception of high-sensitivity C-reactive protein [CRP]) at each visit (AS0009 Week 24, 36, 48, 60, 72, 84, 96, 108, 120, 132, 144, 156, 168, 180, 192, 204, 208, SFU).
- Change from AS0008 Baseline in vital signs (pulse, temperature and blood pressure) (AS0009 Entry Visit [EV], Week 4, 8, 12, 24, 36, 48, 60, 72, 84, 96, 108, 120, 132, 144, 156, 168, 180, 192, 204, 208, Completion/ET, SFU) and body weight (AS0009 EV, Week 12, 24, 36, 48, 60, 72, 84, 96, 108, 120, 132, 144, 156, 168, 180, 192, 204, 208, SFU).

Note that the change from AS0009 EV variables specified in the protocol will not be reported, since the EV assessment is made after 36 or 48 weeks of bimekizumab treatment and there is unlikely to be any further important change.

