3.5 Mapping of assessments

Study assessments at an Early Termination (ET) visit where the visit date is within the protocol-defined visit window of a scheduled site visit will be mapped to that scheduled site visit (this does not include home visits). Visit windows will be calculated relative to the date of first dose in AS0009 (planned at the AS0009 EV), but if the dose was missed at that visit, the date of the AS0009 EV will be used instead. The following rules will also be applied:

- If there is an existing scheduled site visit in the window, and the specific assessment was performed at that scheduled site visit, then the relevant assessments at the ET visit will be mapped to the next scheduled site visit (regardless of whether this is within the protocol-defined visit window for that site visit).
- Study assessments at an ET visit that does not fall into the protocol-defined visit window of a scheduled site visit will be assigned to the next scheduled site visit after the date of the ET visit (regardless of whether this is within the protocol-defined visit window for that site visit).
- Mapping of an assessment to a scheduled visit will occur regardless of whether the assessment was planned to be conducted at that visit (with the exception of ADAb). For ADAb however, data will only be mapped to scheduled site visits where ADAb levels are planned to be measured. Any PK samples taken at the same ET visit will be mapped to the same scheduled visit as the ADAb.

- Additional rules regarding visit mapping are provided in [Section 8.1.5](#) for BASMI and [Section 9.1](#) and [Section 9.2](#) for PK and ADA_b summaries respectively.

Unscheduled assessments where the visit date is within the protocol-defined visit window of a scheduled site visit will be mapped to that scheduled site visit (this does not include home visits). Visit windows will be calculated relative to the date of first dose in AS0009. But if the dose was missed at that visit, the date of the AS0009 EV will be used instead. The following rules will also be applied:

- If there is an existing assessment with a non-missing response (from a scheduled site visit or ET visit) in the window, the assessment will be left as unscheduled.
- Unscheduled assessments which do not fall within a protocol-defined visit window based on time since first dose (or date of AS0009 EV if the first dose was missed) will be left as unscheduled.

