- Unscheduled assessments obtained at specific time points (e.g., vital signs) will only be mapped to a scheduled site visit for the equivalent time point. Thus, if an assessment falls within the protocol-defined visit window of a scheduled site visit but the scheduled visit does not have a corresponding time point, the measurement will be left as unscheduled (e.g., if the unscheduled time point was ‘1 HOUR POST DOSE’ this will not be mapped to a visit at which only ‘PRE DOSE’ time points are scheduled).
- Unscheduled PK and ADA_b assessments may also be mapped to a scheduled site visit if the visit date is within the protocol-defined visit window of that visit. For ADA_b this will only apply to scheduled site visits where ADA_b levels are planned to be measured. For any PK samples obtained at the same unscheduled visit, these will be mapped to the same scheduled visit as the ADA_b.

If there are multiple unscheduled assessments in a specific visit window, the first non-missing assessment will be mapped to the scheduled visit and used for summary statistics or frequency counts. Similarly, if there are multiple scheduled assessments performed on the same visit date, the first non-missing assessment will be used for summary statistics or frequency counts.

Assessments will be reported according to the planned Schedule of Assessments ([Table 2–1](#)) and each scheduled visit summary will include actual data and any data mapped from an ET visit to that scheduled visit. The final visit will be labeled “Week 208”. Data obtained at scheduled visits will be reported as per the database (i.e., these will not be remapped as described above).

Assessments mapped to visits at which the assessment was not planned, unscheduled visits and unscheduled assessments which are not mapped to scheduled visit at which the assessment was planned will be listed only.

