10.3 Clinical laboratory evaluations

The routine clinical laboratory evaluations specified in [Table 10–6](#) will be summarized. If any additional analytes are also recorded they will be listed only.

Table 10–6: Laboratory measurements

Hematology	Biochemistry	Urinalysis
Basophils	Calcium	Urine dipstick for pregnancy testing ^a
Eosinophils	Chloride	Urinalysis ^b
Lymphocytes	Magnesium	
Atypical lymphocytes	Potassium	
Monocytes	Sodium	
Neutrophils	Glucose (random)	
Hematocrit	BUN	
Hemoglobin	Creatinine	
MCH	AST	
MCHC	ALT	
MCV	ALP	
Platelet count	GGT	
RBC count	Total bilirubin	
WBC count	LDH	
	Total cholesterol	
	Uric acid	
	CRP	

ALP=alkaline phosphatase; ALT=alanine aminotransferase; AST=aspartate aminotransferase; BUN=blood urea nitrogen; CRP=high sensitivity C-reactive protein; GGT=gamma glutamyltransferase; LDH=lactate dehydrogenase; MCH=mean corpuscular hemoglobin; MCHC=mean corpuscular hemoglobin concentration; MCV=mean corpuscular volume

^a A urine pregnancy test will be performed for women of childbearing potential if there is a suspicion of pregnancy. A positive urine pregnancy test should always be confirmed with a serum pregnancy test.

^b These measurements will be performed only if a urinalysis is required for safety reasons.

Separate summary tables for hematology and biochemistry variables will be provided, based on central laboratory data only, from scheduled visits (including the SFU visit). Observed values and changes from AS0009 Laboratory Baseline will be summarized, by treatment group at completion of AS0008 and overall. CRP will be summarized separately as described in [Section 8](#).

In the case where laboratory values (with the exception of CRP) are below the LLOQ, then these will be set to the midpoint between 0 and the LLOQ for the purpose of summarizing the data and calculating changes from Baseline. The original value will be reported in any listings.

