Summary tables of the number and percentage of subjects experiencing at least 1 on-treatment markedly abnormal value during the Treatment Period (including unscheduled and repeat assessments, but excluding any measurements that occurred prior to the first administration of study medication in AS0009 or more than 140 days after the last administration of study medication) for each hematology and biochemistry variable will be presented by treatment group at completion of AS0008 and overall. Markedly abnormal values for hematology and biochemistry are defined in [Table 10-7](#) and [Table 10-8](#).

Tables of markedly abnormal laboratory data subject numbers will be provided including all values classified as markedly abnormal at scheduled and unscheduled visits. For all outputs presenting markedly abnormal laboratory values, only central laboratory data will be included.

Table 10-7: Definitions of markedly abnormal hematology values

Variable (SI Units)	Markedly Abnormal Definition	
	Low	High
Hemoglobin (g/L)	<80	>40 above ULN
Lymphocytes ($10^9/L$)	<0.5	>20.0
Neutrophils ($10^9/L$)	<1.0 ^a	N/A
Platelets ($10^9/L$)	<50	N/A
Leukocytes ($10^9/L$)	<2.0	>100

N/A=not applicable; ULN=upper limit of normal

Data source: modified from Appendix Rheumatology Common Toxicity Criteria v.2.0 presented in Woodworth et al, 2007

^a Withdrawal criteria for neutrophils is <0.5

Table 10-8: Definitions of markedly abnormal biochemistry values

Variable (SI Units)	Markedly Abnormal Definition	
	Low	High
ALP	N/A	>5.0 x ULN
ALT	N/A	>5.0 x ULN

Table 10–8: Definitions of markedly abnormal biochemistry values

Variable (SI Units)	Markedly Abnormal Definition	
	Low	High
AST	N/A	>5.0 x ULN
Total bilirubin	N/A	>3.0 x ULN
GGT	N/A	>5.0 x ULN
Creatinine (umol/L)	N/A	>3.0 x ULN or >3 x Baseline value ^a
Glucose (mmol/L)	<2.2	>13.9
Calcium (mmol/L)	<1.75	>3.1
Magnesium (mmol/L)	<0.4	>1.23
Potassium (mmol/L)	<3.0	>6.0
Sodium (mmol/L)	<130	>155
Total cholesterol (mmol/L)	N/A	>10.34

ALP=alkaline phosphatase; ALT=alanine aminotransferase; AST=aspartate aminotransferase; GGT=gamma glutamyl transferase; N/A=Not applicable; ULN=upper limit of normal.

^a The markedly abnormal definitions for creatinine are based on the logical OR; if either criterion is met the creatinine value will be designated as abnormal high.

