A summary of the number and percentage of subjects with a given Common Terminology Criteria for Adverse Events (CTCAE) grade (0, 1, 2, 3 or 4) based on minimum/maximum on-treatment value in AS0009 (including unscheduled and repeat assessments, but excluding any measurements that occurred prior to the first administration of study medication in AS0009 or more than 140 days after the last administration of study medication), will be presented by laboratory variable and treatment group at completion of AS0008. This summary will be provided only for selected laboratory variables and using central laboratory data only.

Definitions of CTCAE grades are given in [Table 10–9](#) and [Table 10–10](#).

A shift table of the number and percentage of subjects experiencing CTCAE grade 0, 1, 2, 3 or 4 values (as applicable) at AS0009 Laboratory Baseline to minimum/maximum post-AS0009 Laboratory Baseline CTCAE grade will be presented by laboratory variable and treatment group at completion of AS0008. The minimum/maximum post-AS0009 Laboratory Baseline CTCAE grade will include all scheduled and unscheduled on-treatment central laboratory assessments (excluding any measurements that occurred prior to the first administration of study medication in AS0009 or more than 140 days after the last administration of study medication).

Table 10–9: Definitions of CTCAE grade by hematology parameter

Parameter (unit)	Definition	Unit	Grade 1	Grade 2	Grade 3	Grade 4
Hemoglobin	Low	g/L	100-<LLN	80-<100	<80	N/A
Hemoglobin ^a	High	g/L	>0-20 above ULN, or >0-20 above Baseline if Baseline is above ULN	>20-40 above ULN, or >20-40 above Baseline if Baseline is above ULN	>40 above ULN, or >40 above Baseline if Baseline is above ULN	N/A
Platelets	Low	10 ⁹ /L	75-<LLN	50-<75	25-<50	<25
WBC	Low	10 ⁹ /L	3-<LLN	2-<3	1-<2	<1
WBC	High	10 ⁹ /L	N/A	N/A	>100	N/A
Lymphocytes	Low	10 ⁹ /L	0.8-<LLN	0.5-<0.8	0.2-<0.5	<0.2
Lymphocytes	High	10 ⁹ /L	N/A	>4-20	>20	N/A
Neutrophils	Low	10 ⁹ /L	1.5-<LLN	1.0-<1.5	0.5-<1.0	<0.5

LLN=lower limit of normal, ULN=upper limit of normal.

^a The CTCAE grade definitions to be applied are dependent on the Baseline hemoglobin value. If the Baseline value is >ULN then the criteria relative to Baseline are applicable; otherwise the criteria relative to ULN are applicable.

Table 10–10: Definitions of CTCAE grade by biochemistry parameter

Parameter (unit)	Definition	Unit	Grade 1	Grade 2	Grade 3	Grade 4

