Creatinine ^a	High	umol/L	>1-1.5 x Baseline or >ULN-1.5 x ULN	>1.5-3.0 x Baseline or >1.5 – 3.0 x ULN	>3.0 x Baseline or >3.0 – 6.0 x ULN	>6.0 x ULN
Sodium	Low	mmol/L	130-<LLN	N/A	120-<130	<120
Sodium	High	mmol/L	>ULN-150	>150-155	>155-160	>160
Potassium ^b	Low	mmol/L	3.0-<LLN	3.0-<LLN	2.5-<3.0	<2.5
Potassium	High	mmol/L	>ULN-5.5	>5.5-6.0	>6.0-7.0	>7.0
Calcium	Low	mmol/L	2.0-<LLN	1.75-<2.0	1.5-<1.75	<1.5
Calcium	High	mmol/L	>ULN-2.9	>2.9-3.1	>3.1-3.4	>3.4
Magnesium	Low	mmol/L	0.5-<LLN	0.4-<0.5	0.3-<0.4	<0.3
Magnesium	High	mmol/L	>ULN-1.23	N/A	>1.23-3.30	>3.30
Cholesterol	High	mmol/L	>ULN-7.75	>7.75-10.34	>10.34-12.92	>12.92

LLN=lower limit of normal, ULN=upper limit of normal.

^a The CTCAE grade definitions for creatinine are based on the logical OR; the highest applicable CTCAE grade should be assigned to a specific creatinine value.

^b Note that subjects who meet the decreased potassium criterion of $3.0 < \text{LLN}$, which is specified as the decreased potassium lab criterion for both CTCAE Grade 1 and Grade 2, will be counted as Grade 2.

The number and percentage of subjects with elevated liver function tests will be presented by treatment group at completion of AS0008 and overall, using on-treatment assessments (excluding any measurements that occurred prior to the first administration of study medication in AS0009 or more than 140 days after the last administration of study medication) from all visits in AS0009 including those at AS0009 Laboratory Baseline, unscheduled, ET and SFU visits. Assessments performed at both central and local laboratories will be included. Each subject will be counted once only. The number and percentage of subjects in the following categories at any time during the study will be presented:

- AST: $>3\times\text{ULN}$, $>5\times\text{ULN}$, $>8\times\text{ULN}$, $>10\times\text{ULN}$, $>20\times\text{ULN}$.
- ALT: $>3\times\text{ULN}$, $>5\times\text{ULN}$, $>8\times\text{ULN}$, $>10\times\text{ULN}$, $>20\times\text{ULN}$.
- AST or ALT: $>3\times\text{ULN}$, $>5\times\text{ULN}$, $>8\times\text{ULN}$, $>10\times\text{ULN}$, $>20\times\text{ULN}$.
- Total bilirubin: $>1.5\times\text{ULN}$, $>2\times\text{ULN}$.
- ALP: $>1.5\times\text{ULN}$.

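### Does SAP 3.3 wrongly let an unscheduled early blood sample stand in for Week 12 as the AS0009 Laboratory Baseline?

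*SAP*

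**What the plan says.** Because the laboratory vendor changed between AS0008 and AS0009, SAP 3.3 gives haematology and biochemistry a new reference, "defined as the earliest post-EV value recorded in AS0009 at or prior to AS0009 Week 12 (excluding any local laboratory measurements". CRP is excepted because its values were calibrated across the two vendors. Local results have no Baseline at all. SAP 3.10 restates the rule more briefly, without the post-entry condition or the local-laboratory exclusion.

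SAP 3.5 covers visit assignment: "Unscheduled assessments where the visit date is within the protocol-defined visit window of a scheduled site visit will be mapped" to that visit. A sample outside every window, or in a window that already holds a value, stays unscheduled. The section ends by saying that values mapped to a visit where the test was not planned, and also "unscheduled visits and unscheduled assessments which are not mapped to scheduled visit at which the assessment was planned will be listed only".

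On use of the Baseline:

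- SAP 2.2.1.3 plans laboratory change, "with the exception of high-sensitivity C-reactive protein [CRP]) at each visit (AS0009 Week 24, 36, 48" and so on, which fits Week 12 as the usual Baseline.
- SAP 10.3 builds the hematology and biochemistry summaries "based on central laboratory data only, from scheduled visits (including the SFU visit".
- Three criteria depend on Baseline: creatinine markedly abnormal, ">3.0 x ULN or >3 x Baseline value" (Table 10-8); the creatinine CTCAE grades, for example Grade 1, ">1-1.5 x Baseline or >ULN-1.5 x ULN" (Table 10-10); and high haemoglobin, "If the Baseline value is >ULN then the criteria relative to Baseline are applicable; otherwise the criteria relative to ULN are applicable" (Table 10-9, footnote a).

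Protocol Table 5-1 and Section 8.2 list no safety blood draw at Weeks 4 and 8. Protocol 9.4 sends unscheduled tests to the central laboratory. Protocol 8.15 allows such a sample when medically indicated and also mentions repeating a specimen after a collection or analysis problem.

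**The concern.** Two things look wrong. First, the rule takes the earliest value and bars only local results, so a central sample drawn at, say, Week 6 for a suspected abnormality becomes the reference for the rest of the study. A later recurrence of the same abnormality would then show as no change and no shift. Second, SAP 3.5 appears to confine that same sample to listings, so two programmers could derive different Baselines from the same data. The outputs at stake are change from Laboratory Baseline, the CTCAE shift table, and the creatinine and high-haemoglobin criteria that refer to Baseline. Since the study is open-label and has had an interim analysis, a subject-level choice of Baseline should not depend on who programs it.

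**Working it through.** The documents give no figure to reproduce, so the check sets the two rules side by side and then tests how much the choice can matter.

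**Which samples are caught.** Take first dose as day 1, so Weeks 4, 8 and 12 fall on days 29, 57 and 85, each with a window of ±7 days (SAP Table 2-1, footnote a). With the Week 12 sample on day 85, earlier post-entry days run from 2 to 84, which is 83 days:

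- Week 4 window, days 22 to 36: 15 days, no laboratory test planned.
- Week 8 window, days 50 to 64: 15 days, no laboratory test planned.
- Week 12 window before the visit, days 78 to 84: 7 days, with a scheduled value present.
- The rest: 83 − 15 − 15 − 7 = 46 days. Of these, days 2 to 8 lie within 7 days of Entry; if an Entry value exists, the sample still stays unscheduled.

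A central sample on any of the 83 days qualifies as Baseline under 3.3. On a literal reading of 3.5, a sample on any of the 83 days is for listing only.

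**Whether 3.5 governs Baseline.** Three points in the SAP say it does not.

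1. Section 3.5 is about mapping values to visits and about by-visit summaries. Section 3.3 is the only section that derives Baseline.
2. The words in 3.3 that admit values before Week 12 have almost no use unless unscheduled samples count, since nothing is scheduled in that interval.
3. The listing rule cannot be a general ban. SAP 10.3 expressly brings unscheduled values into the markedly abnormal, CTCAE worst-grade, CTCAE shift, liver-test and Hy's Law outputs.

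An analyst reading the sections together would use the early central value as Baseline and leave it out of the by-visit rows.

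**What the choice can do.** All values below are assumed. Creatinine is in µmol/L with ULN 110 (3 × ULN = 330), haemoglobin in g/L with ULN 170, and neutrophils in 10⁹/L with LLN at or below 2.5.

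| Early / Week 12 / later | Early value as Baseline | Week 12 as Baseline |
|---|---|---|
| Neutrophils 0.8 / 2.5 / 0.7 | 0.7 − 0.8 = −0.1; Grade 3 to 3 | 0.7 − 2.5 = −1.8; Grade 0 to 3 |
| Creatinine 150 / 80 / 245 | 245/150 = 1.63 and 245/110 = 2.23; Grade 2, not markedly abnormal | 245/80 = 3.06; Grade 3, markedly abnormal |
| Creatinine 60 / 80 / 185 | 185/60 = 3.08; Grade 3, markedly abnormal | 185/80 = 2.31 and 185/110 = 1.68; Grade 2, not markedly abnormal |
| Haemoglobin 175 / 160 / 192 | 192 − 175 = 17 above Baseline; Grade 1 | 192 − 170 = 22 above ULN; Grade 2 |

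The two creatinine rows go in opposite directions, so the rule has no fixed bias. Each row needs an early central sample, a materially different Week 12 value and a later value in a limited band.

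**What a scheduled Week 12 Baseline would cost.** Take neutrophils 0.8 early, 2.5 at Week 12 and normal afterwards. Under 3.3 the shift table shows Grade 3 to 0. With Week 12 as Baseline it shows 0 to 0, and the early event disappears from that table. In addition, under 3.3 no central post-entry value comes before Baseline, so the Baseline-relative creatinine and haemoglobin criteria are defined for every such value. With Week 12 as Baseline, early values would still enter the worst-grade and markedly abnormal tables but with no Baseline before them, and the SAP would need an added rule, such as grading them against ULN only.

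**How many subjects.** The documents give no count. Assumed rates of 1%, 3% and 5% of 285 give 2.85, 8.55 and 14.25, or about 3, 9 and 14 subjects.

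**The case for a change.** The strongest case for a change is that a sample drawn because something looked abnormal is a poor reference point, that Week 12 is plainly the usual Baseline, and that a sentence or two would settle the matter before anyone has to choose with data in view. SAP 3.10 does not help, because it omits two of the conditions in 3.3.

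Part of this stands. The SAP does not say how the listing rule in 3.5 relates to 3.3, and a cross-reference would be tidy.

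The rest carries less weight. Not every early sample follows an abnormality; some only repeat a failed specimen. The laboratory reference in protocol 13.3.1 was the AS0009 entry value, and the earliest result from the new vendor is the closest available to it, so moving to Week 12 goes further from the protocol. The definition is not an open choice either: SAP 13.1.2 shows it in Amendment 1, and Amendment 2 is the one written after the interim results were reviewed (SAP 13.2.1). The interim covered every output except those on COVID-19 (SAP 4.3) and was presumably built on this rule. A new Baseline could make the final laboratory tables disagree with the interim ones.

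The short form in 3.10 is a clerical matter. Entry laboratory values are AS0008 Week 48 results that need not be recorded on the AS0009 eCRF (protocol 8.1), and the local-laboratory exclusion stands in 3.3, the governing section.

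**Conclusion.** No change is needed. The wording does let an unscheduled central sample become Laboratory Baseline, but that is how 3.3 is meant to work, and the apparent conflict with 3.5 goes away once each section is read for its purpose. What remains is a missing cross-reference that analysts can fill sensibly, and a choice between two workable Baselines, each of which loses something.

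The reach is small. Only laboratory change, the CTCAE shift table and the Baseline-relative creatinine and high-haemoglobin criteria could differ. They would differ only for subjects with an early central sample, about 3 to 14 of up to 285 on assumed rates of 1% to 5%. These are descriptive results for other safety variables. The fixed-threshold, liver-test and Hy's Law tables, and the worst-grade table for parameters not graded against Baseline, are the same under either choice and still show the early value. This conclusion rests on early central samples being uncommon, which the visit schedule makes likely but the documents do not quantify. A high rate would increase the count but would not remove the trade-off.
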